The purpose of this Statistical Reporting and Analysis Plan is to describe the planned analyses and outputs to be included in the Clinical Study Report for Protocol 207872.

1 Summary of Key Protocol Information

This proof of principal (PoP) single centre, randomised, examiner blind, four-treatment arm, parallel design study will be used to evaluate and compare the stain build up of two 0.454% stannous fluoride (SnF₂)/5% sodium tripolyphosphate (STP) dentifrices of differing abrasivity levels, with a marketed standard fluoride dentifrice and a marketed SnF₂ dentifrice.

Stain will be assessed following a full professional dental prophylaxis, at intervals over a 4 week treatment period, using an established clinical measure of extrinsic dental stain - the MacPherson modification [Macpherson, 2000] of the Lobene stain index [Lobene, 1968] (MLSI). Subjects will be stratified by pre-prophylaxis MLSI score (total MLSI Area x Intensity (A×I) for the facial surfaces of the 12 anterior teeth) and smoking status.

The study will be conducted in healthy subjects, aged 18-65 years with a minimum of 16 natural teeth (including the 12 anterior teeth) and in good general health, with a propensity for extrinsic dental stain (in the opinion of the examiner) on the facial surfaces of the anterior teeth.

1.1 Study Design

This is a single-centre, examiner-blind, randomised, four treatment, parallel group study, stratified by baseline total MLSI (A×I) score for the facial surfaces of at least 11 of the 12 anterior teeth (<45 (low); ≥45 (high)) and smoking status (smoker; non smoker). A single dental examiner will perform a full MLSI assessment of the area and intensity of extrinsic dental stain on the facial surfaces of the 6 maxillary and 6 mandibular anterior teeth (universal numbering: 6-11 and 22-27), and the lingual surfaces of the 6 mandibular anterior teeth (universal numbering: 22-27), at baseline (Visit 2), and following 2 and 4 weeks twice daily brushing (Visits 3 and 4).

Potential subjects will be pre-screened via telephone and later attend a screening visit during which they will give their written informed consent to participate in the study. Demography, medical history and concomitant medications will be recorded, followed by an oral examination. This will include an oral soft tissue (OST) examination, a full oral hard tissue (OHT) examination and a visual MLSI stain assessment. Subjects deemed (in the opinion of the examiner) to have a sufficient level of extrinsic dental staining (assessed to be formed due to ingestion of food or drinks, or use of tobacco products) on the facial surfaces of the scorable anterior (maxillary and mandibular) teeth, as well as meeting all other study criteria, will be considered as eligible to proceed with the study. Eligible subjects will continue to use

their own dentifrice at home until their baseline visit. Prior to the baseline visit, subjects will be asked to abstain from oral hygiene for at least 6 hours.

At baseline, each subject will undergo an OST and a full OHT, and then brush their anterior teeth for 30 seconds using a wetted toothbrush (with tap water), prior to undergoing a full MLSI stain assessment. Subjects with a sufficient level of extrinsic dental stain (in the opinion of the examiner) on the facial surfaces of the scorable anterior (maxillary and mandibular) teeth, who continue to meet all study criteria, will be stratified (based on pre-prophylaxis baseline total MLSI (A×I) score and smoking status) and randomised to treatment. The stratification factor will give rise to four strata:

- MLSI Score High (≥ 45), Smoker
- MLSI Score Low (< 45), Smoker
- MLSI Score High (≥ 45), Non Smoker
- MLSI Score Low (< 45), Non Smoker

A dental hygienist will professionally clean each subject's teeth using a conventional dental prophylaxis paste followed by flossing (carried out by the hygienist) to remove all visible stain, plaque, debris, and all sub- and supra-gingival calculus from the anterior teeth. A second dental examiner will confirm all sub- and supra-gingival calculus, visible stain (Total MLSI (A×I) = 0), plaque and debris has been removed from the facial, palatal/lingual surfaces of the anterior teeth (visually and by tactile assessment using a dental explorer). Subjects will then be requested to brush twice daily (morning and evening) with their allocated study dentifrice for the next 4 weeks. They will receive verbal and written product usage instructions. First product use will be supervised on site, with a further supervised brushing at Visit 3. Subjects will be asked to record each product use in a diary, and note any significant changes to diet or smoking status, medications and health during the course of the study, and confirmed by the site at each visit.

Subjects will return to the site at Visits 3 and 4, having abstained from oral hygiene for at least 6 hours prior to their visit. Subjects will brush their anterior teeth for 30 seconds using a wetted toothbrush, prior to undergoing a full MLSI stain assessment. Subjects will be asked to bring their study dentifrice, toothbrush and completed diary card to each visit to facilitate compliance checks.

Randomised subjects who request so will be offered a full mouth dental prophylaxis on completion of Visit 4 procedures, or on completion of the visit where they exit the study.

Repeat examinations will be performed by the dental examiner at each full MLSI assessment visit. Ten subjects will be randomly selected for repeat examinations across each assessment window (a total of 30 repeat examinations over the duration of the study) at Visits 2 (pre-prophylaxis), 3 and 4. There will be a minimum of 10 minutes, and a maximum of 30 minutes between repeatability examinations.

Study Schedule

Procedure	Pre-screening	Visit 1 Screening	Visit 2 Baseline (Day0)	Visit 3 Week 2 (Day14 ± 2)	Visit 4 Week 4 (Day28 ± 2)
Telephone Screening of Subjects	✓				
Inform Consent		✓			
Demographics, Medical History, Smoking Status		✓			
Current / Concomitant Medication		✓	✓	✓	✓
Oral Soft Tissue (OST) Examination		✓	✓		
Full Oral Hard Tissue (OHT) Examination		✓	✓		
Visual MLSI Stain Assessment		✓			
Inclusion / Exclusion Criteria		✓	✓		
Eligibility		✓	✓		
Brush Anterior Teeth for 30 Seconds with Tap Water Prior to Stain Assessment			✓	✓	✓
Pre-prophylaxis Full MLSI Stain Assessment of the Anterior Teeth ¹			✓		
Stratification / Randomisation			✓		
Dental Prophylaxis ²			✓		
Post-prophylaxis Visual MLSI Stain Assessment			✓		
Full MLSI Stain Assessment ¹				✓	✓
Dispense Study Dentifrice, Timer, Toothbrush and Diary/Instructions Card			✓		
Supervised Brushing on Site			✓ ₃	✓	
Adverse Events			✓	✓	✓
Incidents			✓ ₄	✓	✓
Subject Adherence and Continuance				✓	✓
Diary Compliance Check ⁵				✓	✓
Return Dentifrice, Toothbrush and Diary Card				✓	✓
Post Treatment Dental Prophylaxis					✓ ₆
Study End					✓

1. Ten subjects will be randomly selected for repeat examinations across each assessment window (a total of 30 repeat examinations over the duration of the study).
2. AEs will be recorded from and including dental prophylaxis onwards.
3. Time of first brushing will be captured to distinguish dentifrice AEs from prophylaxis AEs.
4. Incidents will be collected from first use of the tooth brush, prior to stain assessment.
5. Time of each brushing occasion in addition to missed/additional brushings, and changes to smoking status will be captured in the subject diary.
6. Once all efficacy assessments have been completed randomised subjects who request so will be given a full dental prophylaxis, and will be recorded in the eCRF

1.2 Study Objectives

Objectives	Endpoints
Primary Objective	Primary Endpoint
To evaluate and compare the build up of extrinsic tooth stain, as measured by overall MLSI (A×I), of two experimental 0.454% SnF ₂ / 5% STP dentifrices with that of a marketed standard fluoride dentifrice, after 4 weeks twice daily use.	Overall MLSI at week 4
Secondary Objectives	Secondary Endpoints
To evaluate and compare the build up of extrinsic tooth stain, as measured by overall MLSI (A×I), of two experimental 0.454% SnF ₂ / 5% STP dentifrices with that of a marketed SnF ₂ dentifrice, after 4 weeks twice daily use.	Overall MLSI at week 4.
To evaluate and compare the build up of extrinsic tooth stain, as measured by overall MLSI (A×I), of a marketed SnF ₂ dentifrice with that of a marketed standard fluoride dentifrice, after 4 weeks twice daily use.	Overall MLSI at week 4.
Exploratory Objectives	Exploratory Endpoints
To evaluate and compare the build up of extrinsic tooth stain, as measured by overall MLSI (A×I), of an experimental 0.454% SnF ₂ / 5% STP, 2.0% abrasive silica dentifrice with that of an experimental 0.454% SnF ₂ / 5% STP, 3.5% abrasive silica	Overall MLSI at week 4.

Objectives	Endpoints
dentifrice, after 4 weeks twice daily use.	
To evaluate and compare the build up of extrinsic tooth stain , as measured by overall MLSI (A×I), of two experimental 0.454% SnF ₂ / 5% STP dentifrices with that of a marketed standard fluoride dentifrice and a marketed SnF ₂ dentifrice, after 2 weeks twice daily use.	Overall MLSI at week 2.
To evaluate and compare the build up of extrinsic tooth stain, as measured by overall Interproximal (Distal + Mesial) MLSI, of two experimental 0.454% SnF ₂ / 5% STP dentifrices with that of a marketed standard fluoride dentifrice and a marketed SnF ₂ dentifrice, after 2 and 4 weeks twice daily use.	Overall Interproximal (Distal + Mesial) MLSI at weeks 2 and 4.
To evaluate and compare the build up of extrinsic tooth stain, as measured by overall MLSI Area (A), of two experimental moderate abrasivity 0.454% SnF ₂ / 5% STP dentifrices with that of a marketed standard fluoride dentifrice and a marketed SnF ₂ dentifrice, after 2 and 4 weeks twice daily use.	Overall MLSI Area at weeks 2 and 4.
To evaluate and compare the build up of extrinsic tooth stain, as measured by overall MLSI Intensity (I), of two experimental moderate abrasivity 0.454% SnF ₂ / 5% STP dentifrices with that of a marketed standard fluoride dentifrice and a marketed SnF ₂ dentifrice, after 2 and 4 weeks twice daily use.	Overall MLSI Intensity at weeks 2 and 4.

1.3 Treatments

	Test Product 1	Test Product 2	Reference Product 1	Reference Product 2
Product Name	Experimental dentifrice containing 0.454% SnF ₂ / 5% STP; 2.0% abrasive silica (RDA~58)	Experimental dentifrice containing 0.454% SnF ₂ / 5% STP; 3.5% abrasive silica (RDA~77)	Dentifrice containing 1000ppm fluoride as Sodium Monofluorophosphate (SMFP; Colgate Cavity Protection [®] , Canada Marketed dentifrice) moderate abrasivity (RDA~80)	Dentifrice containing 0.454% SnF ₂ (Sensodyne Complete Protection, Canada Marketed dentifrice) higher abrasivity (RDA~120)
Short Product Name	Test dentifrice (RDA~58)	Test dentifrice (RDA~77)	Reference dentifrice (RDA~80)	Reference dentifrice (RDA~120)
Product Formulation Code (MFC)	CCI	CCI	Commercially Available	Commercially Available

1.4 Sample Size Calculation

A sufficient number of subjects will be screened to randomise at least 220 subjects to ensure 200 evaluable subjects complete the study. This will ensure approximately 50 evaluable subjects per treatment arm. This study has not been formally powered to make any claims, and is appropriately sized as a PoP study for the purpose of observing meaningful trends.

2 Planned Analyses

2.1 Interim Analysis

No interim analysis is planned.

2.2 Final Analyses

The final planned primary analyses will be performed after the completion of the following sequential steps:

1. All subjects have completed the study as defined in the protocol.

2. All required database cleaning activities have been completed and database has been locked.
3. All criteria for unblinding the randomisation codes have been met and the randomisation codes have been distributed.

3 Considerations for Data Analyses and Data Handling Conventions

3.1 Baseline Definition

For all endpoints the baseline value will be the latest pre-dose assessment with a non-missing value.

3.2 Subgroups/Stratifications

Eligible subjects will be stratified by baseline total MLSI (A×I) score (Low: <45; High: ≥45) and smoking status into four strata in study treatment randomization.

- MLSI Score High (≥45), Smoker
- MLSI Score Low (<45), Smoker
- MLSI Score High (≥45), Non Smoker
- MLSI Score Low (<45), Non Smoker

Subjects identified as being in the wrong strata will be placed in correct strata prior to analysis and will also be considered for protocol deviations and potential exclusion from a PP analysis.

3.3 Timepoints and Visit Windows

Time windows required for this study are as the following:

- Visit 2 (Baseline) is minimum 24 hours and maximum two weeks from Visit 1 (Screening)
- Visit 3 (Week 2) is 14 ± 2 Days from Visit 2
- Visit 4 (Week 4) is 28 ± 2 Days from Visit 2

4 Data Analysis

Data analysis will be performed by inVentiv Health Clinical. Prior to database closure a Blind Data Review Meeting (BDRM) will be conducted in which various aspects of the trial will be discussed and agreed. The statistical analysis software used will be SAS version 9.4.

All listings will be produced for all randomized subjects, unless otherwise stated.

4.1 Populations for Analysis

Except otherwise specified, tables described in this section will be produced for all randomised subjects.

4.1.1 Subject Disposition

Screen failures will be defined as subjects who consent to participate in the study but are never subsequently randomised. A summary will be provided of the number of subjects screened and the number of screen failures.

Subject disposition will be summarised as the number and percentage of subjects (out of the number of randomised subjects) who complete the study, with the number who discontinue broken down by reason for discontinuation ([Table 14.1.1](#)). The table will also summarise the number and percent of subjects assigned to each analysis population (defined in Section 2.1.3). The summary will be presented by treatment and overall.

Subject disposition will be listed for randomised subjects ([Listing 16.2.1.1](#)) and non-randomised subjects ([Listing 16.2.1.2](#)) separately.

4.1.2 Protocol Deviations

Important major protocol deviations (including deviations related to study inclusion/exclusion criteria, conduct of the trial, patient management or patient assessment) will be summarised and listed.

Protocol deviations will be tracked by the study team throughout the conduct of the study. All deviations will be reviewed prior to unblinding and closure of the database to ensure all important deviations are captured and categorised.

Major deviations of the protocol procedures identified as liable to influence the efficacy outcome may include the following

- Deviation from the inclusion/exclusion criteria
- Use of prohibited medication
- Not receiving randomised treatment

Further deviations liable to influence the efficacy outcome will be given in the “Review Listing Requirement (RLR)” document and major deviations will be identified in blinded data review stage. The number and percentage of subjects with any major protocol deviations and with each type of major protocol deviations will be presented by treatment ([Table 14.1.2](#)) for randomised subjects and listed in [Listing 16.2.2.1](#). Any minor protocol deviations will be listed similarly ([Listing 16.2.2.2](#)).

4.1.3 Analysis Populations

Six populations are defined below.

Population	Definition / Criteria	Analyses Evaluated
All Screened Subjects	All subjects who enter the study and sign the informed consent form. This population includes screen failures as well as those that are randomised	Disposition, AE listing
Randomised	All subjects who are randomised and may or may not receive the application of the study products.	Protocol violations
Safety	All subjects who are randomised and receive at least one dose of investigational product. The Safety population will be reported by treatment received.	Safety analysis
Intent-to-Treat (ITT)	The 'Intent to treat' (ITT) population will include all subjects who are randomised, receive at least one dose of investigational product and have at least one post-baseline efficacy assessment. The ITT population will be reported by randomised treatment.	MLSI analysis
Per-Protocol (PP)	The 'Per-Protocol' (PP) population will include all subjects in the ITT population who have at least one efficacy assessment considered unaffected by protocol deviations. Efficacy assessments considered affected by protocol deviations will be excluded from PP analysis.	MLSI analysis
Repeatability population	All subjects who have an initial and a repeat stain examination at each full MLSI assessment visit.	MLSI repeatability analysis

The primary population for assessment of efficacy will be the ITT population. A PP analysis will be performed on the primary variable (MLSI at week 4) only if more than 20% of the subjects in the ITT population are excluded from the PP population.

The numbers of subjects excluded from each population broken down by the reason for exclusion will be presented ([Table 14.1.3](#)). Subjects excluded from any of the analysis populations will be listed ([Listing 16.2.3.1](#)).

4.2 Subject Demographics and Other Baseline Characteristics

Demographic and baseline characteristics summaries will be produced for the ITT.

4.2.1 Demographic Characteristics

Categorical demographic variables include sex and race. These variables will be summarised by the number and percentage of subjects with each relevant characteristic ([Table 14.1.4.1](#) for the Safety population, [Table 14.1.4.2](#) for the ITT population). Age will be summarised by the mean, standard deviation (SD), median, minimum and maximum values. Baseline stratification will also be summarised by the number and percentage of subjects in each stratum. All summaries will be presented by treatment, and overall. All demographic information will be listed for randomised subjects ([Listing 16.2.4.1](#)).

4.2.2 General Medical History

Medical history data will be listed for all randomised subjects in [Listing 16.2.4.2](#) with start date and end date or ongoing at the start of study drug. A data listing will also be produced for evaluation of protocol deviations at the blinded data review stage.

4.3 Treatments (Study Product Compliance and, Concomitant Therapies)

4.3.1 Study Product Compliance

Brushing compliance (using study products twice daily) will be listed and checked at the blinded data review stage for evaluation of protocol deviations.

4.3.2 Prior and Concomitant Medication

Prior and concomitant medication/non-drug treatments data will be listed in [Listing 16.2.5.1](#), [16.2.5.2](#). Prior medications are defined as those stopped before the first administration of the study products. Concomitant medications are defined as those ongoing or started on or after the the first administration of the study products.

A data listing will also be produced for evaluation of protocol deviations at the blinded data review stage.

4.4 Analysis of Efficacy

4.4.1 Primary Efficacy Endpoint

4.4.1.1 Primary Efficacy Endpoint Definition

The primary endpoint is the Week 4 overall MLSI (A×I).

Each tooth site will be evaluated for stain level and will be assigned an intensity score (I) and an area score (A) by the examiner. Overall MLSI (A×I) score for each subject at each visit (Baseline, Week 2 and Week 4) is calculated as the mean MLSI (A×I) score over all gingival, body, mesial and distal sites on the facial surfaces of the six maxillary anterior teeth and six mandibular anterior teeth, and the lingual surfaces of the six mandibular anterior teeth. It is

possible that some sites could have missing values, in that case the mean is calculated over all non-missing sites

4.4.1.2 Statistical Hypothesis, Model, and Method of Analysis

Summary statistics including mean, SD, median, min, max will be provided for baseline and Week 4 by randomised treatment group ([Table 14.2.1.1.1](#)). The overall MLSI score at Week 4 will be analysed using analysis of covariance (ANCOVA) with treatment and smoking status (smoker/non-smoker) as factor and pre-prophylaxis baseline overall MLSI score as covariate.

The primary comparisons are

- Test dentifrice (RDA-58) vs. Reference dentifrice (RDA-80)
- Test dentifrice (RDA-77) vs. Reference dentifrice (RDA-80).

All other comparisons associated with secondary and exploratory objectives will also be presented under the same analysis, namely

- Test dentifrice (RDA-58) vs. Reference dentifrice (RDA-120) (secondary)
- Test dentifrice (RDA-77) vs. Reference dentifrice (RDA-120) (secondary)
- Reference dentifrice (RDA-120) vs. Reference dentifrice (RDA-80) (secondary)
- Test dentifrice (RDA-58) vs. Test dentifrice (RDA-77) (exploratory)

Adjusted means of all treatments will be provided. Treatment differences of above mentioned comparisons will be provided together with their 95% CIs and p-values ([Table 14.2.1.1.2](#)). The assumption of residual normality in ANCOVA analysis will be investigated. If violated, data transformation or a non-parametric method (e.g., the Wilcoxon rank sum test) will be applied.

There will be no multiplicity adjustment for treatment comparisons as this study is an exploratory POP study.

Efficacy will be evaluated based on the ranking performance of the study treatments on the stain variables. The minimum requirement will be similar, or lower levels of stain for at least one of the experimental products compared to the standard fluoride dentifrice (Colgate Cavity Protection[®]). The marketed SnF₂ dentifrice (Sensodyne Complete Protection) will be expected to demonstrate a comparable, or statistically significantly better performance on the stain variables versus the experimental products and Colgate Cavity Protection[®].

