- Review inclusion/exclusion criteria.
- Review of the oral care products the subject is currently using to confirm they do not contain any restricted ingredients.

Document Name	207872 Clinical Protocol.doc		
Type	Version	Document Identifier	Effective Date
elido_clinical_doc	5.0; Most-Recent; Effective; CURRENT	090032d580d488e0	30-May-2017 04:37:09
Reason For Issue	Auto Issue		

- Demographics, current/concomitant medications, medical history and smoking status captured.
- Oral examinations including an OST and a full OHT examination.
- Visual MLSI stain assessment of the facial (maxillary and mandibular) surfaces.
- Confirmation of subject eligibility.

Visit 2 - Baseline Visit

The following assessments will be conducted:

- Review of current/concomitant medications.
- Confirmation of subject eligibility and continuance.
- Full OST examination.
- Full OHT examination.
- Supervised brushing of the anterior teeth for 30 seconds using a wetted toothbrush.
- Pre-prophylaxis full MLSI stain assessment of the facial (maxillary and mandibular) and lingual (mandibular) surfaces.
- Stratification (based on total MLSI score of the facial surfaces only) and randomisation.
- Full professional dental prophylaxis.
- Post-prophylaxis visual MLSI stain assessment of the facial (maxillary and mandibular) and lingual (mandibular) surfaces to confirm overall MLSI = 0.
- Dispensation of study dentifrice, toothbrush, timer and diary/instructions card.
- Supervised brushing with subject's allocated dentifrice.
- AEs and Incidents following supervised brushing.

Visit 3 - Week 2

The following assessments will be conducted:

- Subjects return study dentifrice, toothbrush, and diary card to the clinical site.
- Review of current/concomitant medications, AEs and incidents.
- Review of completed diary to confirm timing of each brushing occasion in addition to missed/additional brushings, and potential changes to smoking status.
- Confirmation of subject adherence and continuance. Supervised brushing of the anterior teeth for 30 seconds using a wetted toothbrush.
- Full MLSI stain assessment of the facial (maxillary and mandibular) and lingual (mandibular) surfaces.
- Supervised brushing with subject's allocated dentifrice.
- AEs and Incidents following supervised brushing.

Document Name	207872 Clinical Protocol.doc		
Type	Version	Document Identifier	Effective Date
elido_clinical_doc	5.0; Most-Recent; Effective; CURRENT	090032d580d488e0	30-May-2017 04:37:09

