Stain assessments will be made on the facial and lingual surfaces of the anterior teeth as these surfaces are considered the most aesthetically important with respect to dental stain accumulation. Dental stain largely builds up in the harder to reach interproximal areas, therefore in addition to analysis of the total MLSI (A×I) the interproximal regions have also been given focus as an exploratory objective in this study. As most of the stain is removed from the body and gingival regions, we would expect to see little change in the total gingival MLSI (A×I) and total body MLSI (A×I), therefore, these variables are not being analysed in this study. Furthermore, separate analysis of the facial and lingual surfaces are not of focus in this study. As the facial teeth are the most brushed we would expect to see little stain build up on the facial surfaces in comparison to the lingual surfaces, with little difference expected between the total MLSI (A×I) and total lingual MLSI (A×I).

A single examiner will perform the dental stain assessments for all subjects at the baseline, Week 2 and 4 visits to avoid inter-examiner variability. To assess the repeatability of the stain assessments 30 repeat examinations will be performed by the dental examiner over the duration of the study.

The dosage regimen of twice daily use (morning and evening) will be the same for all subjects, and has been selected based on widely recommended oral hygiene practice, and typical consumer habit.

Document Name	207872 Clinical Protocol.doc		
Type	Version	Document Identifier	Effective Date
elido_clinical_doc	5.0; Most-Recent; Effective; CURRENT	090032d580d488e0	30-May-2017 04:37:09
Reason For Issue	Auto Issue		

Sensodyne Complete Protection has been selected as a reference dentifrice in this study as it is a commercialised SnF₂ containing dentifrice. Colgate Cavity Protection® has been selected as a reference comparator as it is marketed globally, does not contain any ingredients known to impart extrinsic dental stain, and is considered to be representative of a moderate abrasivity standard, daily use fluoride dentifrice. Two recent stain build up studies have been conducted by GSKCH, which contain both the commercialised SnF₂ dentifrice and Colgate Cavity Protection®, providing us with a recent benchmark of relative and expected performance at the Week 4 time-point.

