5.8.1 Randomisation

A unique screening number will identify each subject screened for study participation. Screening numbers will be assigned in ascending numerical order as each subject signs their consent form. Subjects who meet all inclusion and exclusion criteria will be randomised according to the randomisation schedule. Randomisation numbers will be assigned in ascending numerical order as each subject is determined to be fully eligible.

Subjects with a sufficient level of extrinsic dental stain (in the opinion of the examiner) on the facial surfaces of the scorable anterior (maxillary and mandibular) teeth, who continue to meet all study criteria, will be stratified (based on pre-prophylaxis baseline total MLSI (A×I) score and smoking status) and randomised to treatment. The stratification factor will give rise to four strata:

- MLSI Score High, Smoker
- MLSI Score Low, Smoker
- MLSI Score High, Non Smoker

Document Name	207872 Clinical Protocol.doc		
Type	Version	Document Identifier	Effective Date
elido_clinical_doc	5.0; Most-Recent; Effective; CURRENT	090032d580d488e0	30-May-2017 04:37:09
Reason For Issue	Auto Issue		

- MLSI Score Low, Non Smoker

The randomisation list will be prepared using a randomisation block design with an equal allocation to each of the strata. The study site will receive two versions of the randomisation schedule, each in a sealed envelope and clearly marked as either “For Dispensing” or “Emergency Use Only”.

The “For Dispensing” schedule will contain the list of randomisation numbers only and will not include any coded description, just a letter A, B, C or D.

The ‘Emergency Use Only’ randomisation schedule will only be removed from the sealed envelope in an emergency situation (see Section 5.8.3). This schedule will have a randomisation number followed by the letter A, B, C or D. The schedule will have a footnote with a key for A, B, C and D identifying the three treatments.

However, to maintain the blinding of the study as far as possible, all treatment allocations for all randomisation numbers on this randomisation schedule will be masked with scratch-off panels. Only the panels required for the unblinding the particular subject should be removed.

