9.3.2. Primary Analysis

The primary variable will be overall MLSI at Week 4. This variable will be analysed using analysis of covariance (ANCOVA) with treatment and smoking status as factor, and pre-prophylaxis baseline mean MLSI score as the covariate. Adjusted means and treatment differences between the two test products and the marketed standard fluoride dentifrice, and the treatment difference between the marketed SnF₂ dentifrice and the marketed standard fluoride dentifrice will be provided together with their 95% CIs and p-values.

The assumption of residual normality in ANCOVA analysis will be investigated. If violated, data transformation or a non-parametric method (e.g., the Wilcoxon rank sum test) will be applied.

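### The ANCOVA omits the MLSI stratum used in randomisation; adding it costs one degree of freedom and may narrow the intervals by 0% to 3%

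*SAP*

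**What the plan says.** **Randomisation.** SAP 3.2: "Eligible subjects will be stratified by baseline total MLSI (A×I) score (Low: <45; High: ≥45) and smoking status into four strata". The Visit 2 list in protocol 3.1 shows that the MLSI part ignores lingual surfaces: "Stratification (based on total MLSI score of the facial surfaces only) and randomisation". SAP 1.1 allows for an ungradable tooth, with subjects "stratified by baseline total MLSI (A×I) score for the facial surfaces of at least 11 of the 12 anterior teeth". Protocol 5.8.1 describes a "randomisation block design with an equal allocation to each of the strata"; the block size is not given.

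**Analysis.** SAP 4.4.1.2 fits an ANCOVA "with treatment and smoking status (smoker/non-smoker) as factor and pre-prophylaxis baseline overall MLSI score as covariate". Protocol 9.3.2 has the same structure, with "pre-prophylaxis baseline mean MLSI score as the covariate". The synopsis and the footnote to SAP Table 14.2.1.1.2 agree. SAP 4.6 uses the same factors for the exploratory endpoints, each with its own matching baseline.

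**Covariate.** Under SAP 4.4.1.1, overall MLSI is one mean over all non-missing facial and lingual sites.

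**Strata in the analysis.** SAP 3.2 reassigns wrongly stratified subjects to the right stratum before analysis. Only the smoking half of that correction reaches any efficacy model.

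**The concern.** Stratified blocks force balance on the stratifying factors. If a factor predicts the outcome and is left out of the model, the variance it explains stays in the residual. The model then overstates the standard error of the treatment difference, and precision already paid for in the design is lost.

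The covariate and the stratifier are related but not identical. The stratifier is a facial total cut at 45. The covariate is a mean in which one third of the sites are lingual. For the interproximal, area and intensity endpoints the covariate is a different score again.

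Width has some importance here. SAP 4.4.1.2 sets a minimum requirement of similar or lower stain and gives no margin for similar. A wider interval makes a non-significant difference easier to read as similarity, so an overly wide interval is not automatically the safe direction.

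**Working it through.** **1. Figures in the plan.** There is no power calculation, SD or effect size to reproduce. SAP 1.4 gives 200 evaluable subjects, and 200/4 = 50 per arm.

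**2. How much of the stratum the covariate carries.** Sites, from SAP 4.4.1.1: 12 × 4 = 48 facial and 6 × 4 = 24 lingual, 72 in all, so 48/72 = 2/3 are facial. With equal facial and lingual SDs and correlation ρ (both assumed),

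corr(facial mean, overall mean) = (2 + ρ)/√(5 + 4ρ).

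- ρ = 0.3: 2.3/√6.2 = 0.92
- ρ = 0.5: 2.5/√7 = 0.94
- ρ = 0.7: 2.7/√7.8 = 0.97

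The overlap is large but incomplete. A missing tooth adds a small gap, because the stratifier is a total and the covariate a mean. The cut of 45 is 45/48 = 0.94 per facial site with 12 gradable teeth, but 45/44 = 1.02 with 11.

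**3. Cost of the extra term.** The planned model has 6 parameters (intercept, three for treatment, smoking, baseline), leaving 200 − 6 = 194 residual df. Adding the stratum leaves 193. If r is the partial correlation of stratum and outcome given the planned terms,

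SE ratio = √[(1 − r²) × 194/193].

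- r = 0.1: 0.998 (0.2% smaller)
- r = 0.2: 0.982 (1.8% smaller)
- r = 0.3: 0.956 (4.4% smaller)

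Break-even is r = √(1/194) = 0.07.

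**4. Error rate and width.** Simulation: 3,000 trials per scenario with no treatment effect, 200 subjects, four arms, blocks of 4 within the four strata. Assumed, not in the documents: block size, 30% smokers, facial-lingual correlation 0.5 (0.3 in the lingual-only pattern), and full-model R² of 0.15, 0.30 and 0.50. The results at 0.30 and 0.50 are below. The last two columns are mean CI width relative to the planned model.

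| Baseline pattern driving Week 4 | R² | Planned type I error | Planned model SE / empirical SD | Width with stratum added | Width with separate facial and lingual baselines |
|---|---|---|---|---|---|
| Equal slope per site | 0.30 | 5.2% | 0.99 | 1.001 | 1.003 |
| Lingual dominant | 0.30 | 4.6% | 1.03 | 0.995 | 0.960 |
| Lingual only | 0.30 | 4.6% | 1.02 | 0.983 | 0.919 |
| Extra step at the stratum cut | 0.30 | 5.0% | 1.00 | 0.990 | 1.002 |
| Equal slope per site | 0.50 | 5.3% | 1.00 | 1.001 | 1.002 |
| Lingual dominant | 0.50 | 4.7% | 1.01 | 0.987 | 0.912 |
| Lingual only | 0.50 | 4.0% | 1.04 | 0.967 | 0.835 |
| Extra step at the stratum cut | 0.50 | 5.0% | 1.01 | 0.976 | 1.002 |

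Over all scenarios, including R² = 0.15, planned type I error was 4.0% to 5.7% (Monte Carlo SE about 0.4 points) and model SE over empirical SD was 0.98 to 1.04. Adding the stratum gave a relative width of 0.967 to 1.001.

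**5. Scale.** At 50 per arm the 95% CI half-width is about 1.97 × √(2/50) = 0.39 residual SD. A 3.3% narrowing is 0.033 × 0.39 = 0.013 SD. It equals 200/0.967² − 200, about 14 subjects, in the most favourable scenario only.

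**The case against.** The strongest defence is that the plan already adjusts for the stratifier in a better form. A continuous baseline usually carries more information than a two-level cut of it, and the endpoint's own baseline is the standard covariate. This is also an exploratory study that SAP 1.4 says is not formally powered, so a change of at most 3% is unlikely to alter a conclusion. Most of this stands, and it is why the point is minor. It does not explain why smoking status was kept and the MLSI stratum dropped without comment, or why SAP 3.2 corrects an MLSI stratum that no efficacy model uses.

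Three stronger readings are tempting, and the documents do not support them.

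- *A reader might infer that the intervals do not match the design and are invalid.* The continuous baseline prevents that. Type I error stayed near 5%, and any mismatch of note was on the wide side.
- *A reader might take r = 0.3 and conclude that about 19 of 200 subjects are wasted (200/0.956² − 200).* The largest simulated gain, 3.3%, corresponds to r of about 0.26, and most gains were far smaller.
- *A reader might infer that pooling facial and lingual baselines is an error and that the covariate should be replaced by two.* Protocol 3.3 does say that "we would expect to see little stain build up on the facial surfaces in comparison to the lingual surfaces". That describes build-up after prophylaxis, not which pre-prophylaxis surface predicts it. The gain from splitting ran from a 0.3% loss with equal slopes to 16.5% when only lingual baseline mattered. It also depends on baseline SDs. If only lingual baseline predicts, with R² 0.36 and correlation 0.5, the SE gain is about 10% with equal SDs, 6% if the lingual SD is twice the facial, and 4% if it is three times. The documents give neither slopes nor SDs.

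**Conclusion.** The point holds in limited form. One of the two stratification factors is missing from the ANCOVA, and the continuous baseline replaces most but not all of it. The planned intervals keep about nominal error but may be slightly too wide. Adding the stratum narrows them by about 0% to 3%, with a loss of about 0.1% at worst.

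These sizes rest on the assumed correlations, R², smoking proportion and block size. The omission itself rests only on the text. Severity is minor: a free improvement, not a flaw that threatens the conclusions.

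**What to change.** Before unblinding:

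- In SAP 4.4.1.2 and 4.6, the footnote to SAP Table 14.2.1.1.2, protocol 9.3.2 and the protocol synopsis, add the MLSI stratum (low/high, as corrected under SAP 3.2) as a factor beside smoking status.
- Keep each endpoint's own continuous baseline as the covariate. In SAP 4.6 this matters: putting facial and lingual MLSI means in its place would remove the matched interproximal, area and intensity baselines.
- Optionally, pre-specify a sensitivity analysis of the primary endpoint with separate facial and lingual baseline means. Both can be calculated from the Visit 2 scores. The gain may be nil.

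The cost is one degree of freedom, one model term and a few lines of text, with no new data. The protocol edits must go through the sponsor's amendment process. If the protocol is left as it is, the change belongs in SAP section 5.
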